- For summaries at a patient level, all values should be included, regardless of whether they appear in a corresponding visit based summary, when deriving a patient level statistic such as a maximum.
- Baseline will be defined as the last non-missing measurement prior to dosing with study treatment (excluding unscheduled visit). For the re-treatment period for immunotherapy agents then baseline is similarly defined as the last non-missing measurement prior to the first dose on the re-treatment period. For laboratory data, any assessments made on day 1 will be considered pre-dose. Alternatively, if two visits are equally eligible to assess patient status at baseline (e.g., screening and baseline assessments both on the same date prior to first dose with no washout or other intervention in the screening period), the average can be taken as a baseline value. For non-numeric laboratory tests (ie some of the urinalysis parameters) where taking an average is not possible then the best value would be taken as baseline as this is the most conservative. In the scenario where there are two assessments on day 1, one with time recorded and the other without time recorded, the one with time recorded would be selected as baseline. Where safety data are summarised over time, study day will be calculated in relation to date of first treatment.
- Missing safety data will generally not be imputed. However, safety assessment values of the form of "< x" (i.e., below the lower limit of quantification) or > x (i.e., above the upper limit of quantification) will be imputed as "x" in the calculation of summary statistics but displayed as "< x" or "> x" in the listings.
- For missing diagnostic dates, if day and/or month are missing use 01 and/or Jan. If year is missing, put the complete date to missing.
- For missing concomitant medication and AE start dates:
 - If year is missing (or completely missing), do not impute.

- If year is present and months and day are missing; or year and day are present and month is missing, impute as January 1st.
- If year and month are present and day is missing, impute day as first day of the month.
- For missing concomitant medications and AE end dates, the following will be applied:
 - If year is missing (or completely missing), do not impute.
 - If year is present and month and day are missing; or year and day are present and month is missing, impute as December 31st.

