 - If year and month are present and day is missing, impute day as last day of the month.
 - When the patient has died in the same month/year of partial stop date, use date of death.
- For medications, a conservative approach will be followed and events will be assumed to be concomitant unless the end date is before the first dose of IP. If the start and end dates are both missing it is considered concomitant.
- In addition for AEs if, for a partial start date, the AE start date could (when also considering the AE end date) potentially be on the first study treatment date, the AE start date will be imputed with the first study treatment date to assume a "worst case" scenario; e.g. AE from UNK-Jun-2017 to 23-Jul-2017 with the first study treatment date 21-Jun-2017, then the AE start date will be imputed to 21-Jun-2017.

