3.4 Baseline

3.4.1 Prior and concomitant medications

The WHO Drug B3 dictionary will be used for concomitant medication coding.

Any medications taken by the patient prior to the first dose date of study treatment will be considered prior medication.

Any medication taken by the patient at any time after the date of the first dose (including the date of the first dose) of study treatment up to 90 days after last dose will be considered concomitant medication. Any medication that started prior to the first dose of study treatment and ended after the first dose or is ongoing will be considered as both prior and concomitant medication.

For the purpose of inclusion in prior or concomitant mediation summaries, incomplete medication start and stop dates will be imputed as detailed in Section 3.1.3.

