4. ANALYSIS METHODS

4.1 General principles

No hypothesis testing is planned for this single arm study. Each module will be summarised separately.

The general principles as mentioned below will be followed throughout the study:

- Descriptive statistics will be used for all variables, as appropriate, and will be presented separately for each module. Descriptive safety and efficacy data from the STRONG study may be utilized as supporting evidence for health authority considerations.
- Continuous variables will be summarized by the number of observations, mean, standard
 deviation, median, minimum, and maximum. For log transformed data it is more
 appropriate to present geometric mean, coefficient of variation (CV), median, minimum
 and maximum. Categorical variables will be summarized by frequency counts and
 percentages for each category.
- Unless otherwise stated, percentages will be calculated out of the population total.
- Exact CIs for proportions will be calculated using the Clopper-Pearson method.
- For percentiles of survival times based on the Kaplan-Meier method (eg, median survival), CIs will be calculated using the default method available in the SAS LIFETEST procedure (ie, the Klein and Moeschberger extension of the Brookmeyer-Crowley method).
- For point-estimates of survival based on the Kaplan-Meier method (eg, for OS at 12 months), CIs will be calculated using the default method available in the SAS LIFETEST procedure (ie, using Greenwood's estimate of standard error and a log-log transformation).
- For continuous data the mean and median will be rounded to 1 additional decimal place compared to the original data. The standard deviation will be rounded to 2 additional decimal places compared to the original data. Minimum and maximum will be displayed with the same accuracy as the original data.
- For categorical data, percentages will be rounded to 1 decimal place.
- SAS® version 9.3 or higher will be used for all analyses.

Baseline will be the last assessment of the variable under consideration prior to the intake of the first dose of study treatment.

All data collected will be listed.

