- At least one treatment-emergent serious AESI
- At least one treatment-emergent AESI by maximum NCI CTCAE grade
- At least one treatment-emergent AESI causally related to study medication
- At least one treatment-emergent AESI with fatal outcome
- At least one treatment-emergent AESI which required additional treatment with steroids, immunosuppressants and hormone replacement therapy
- Laboratory findings, vital signs and other safety parameters associated with AESI will be summarised as part of the AESI outcome measures.

Length of intervention with steroids, immunosuppressants and/or hormone replacement therapy for AESIs will be calculated based on treatment start and stop dates. Total treatment

times will then be combined for each patient and summarised for patients experiencing at least one treatment-emergent AESI.

The exact 95% CIs around the incidence estimates will also be reported for each AESI type.

A summary of total duration (days) of AESI will be provided. For ongoing AESI, the date of death or data cut-off will be imputed as end date.

Immuno-mediated adverse events

Summaries of treatment-emergent imAEs by AESI category and PT will include number (n) and percentage (%) of patients who have:

- At least one treatment-emergent imAE
- At least one treatment-emergent imAE by outcome
- At least one treatment-emergent imAE leading to treatment interruption or discontinuation
- At least one treatment-emergent serious imAEs
- At least one treatment-emergent imAE by maximum NCI CTCAE grade
- At least one treatment-emergent imAE causally related to study medication
- At least one treatment-emergent imAE with fatal outcome

Subgroup analyses

Subgroup analyses will be conducted for the summary of TEAEs in the following subgroups of the SS:

- Sex (male versus female)
- Age at baseline: <65 vs 65-74 vs ≥75 years of age). This will be determined from the date of birth (BRTHDAT in the DM domain) and baseline visit (VIS_DAT in the VISIT domain) on the eCRF. Patients with a partial date of birth (ie for those countries where year of birth only is given) will have an assumed date of birth of 1st Jan [given year]). Patients with a missing age value will be included using the mean age and categorised accordingly.
- Race: Asian vs non-Asian
- ECOG performance status at baseline: 0-1 vs 2
- Tumor histology: Urothelial (i.e. TCC) vs non-urothelial

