- PDL1: high >=25% vs low <25%. If data is available from the central laboratory, the central laboratory result will be used in the group derivation, otherwise, the local test result will be used.

Subgroup analyses will also be conducted for the summary of OS, ORR and DCR in the following subgroups of the SS:

- Age at baseline: <65 vs 65-74 vs ≥ 75 years of age
- ECOG performance status at baseline: 0-1 vs 2
- Primary tumor location: Bladder vs Renal pelvis and Ureter vs Urethra vs Other
- Stage: III vs IV
- Tumor histology: Urothelial (i.e. TCC) vs non-urothelial
- Previous platinum chemotherapy: platinum vs non-platinum chemotherapy
- Best response to previous therapy (CR vs PR vs SD vs PD)

- Baseline metastases: liver (+/- other visceral or non-visceral metastases) vs lymph node metastases only
- PDL1: high \geq 25% vs low \leq 25%

No formal comparisons will be performed between the subgroups.

Time-to-event analyses

Time-to-event of AESI and imAE:

Time-to-onset of AESI/imAE (by AESI/imAE category) and time-to-intervention with steroids, immunosuppressants and/or hormone replacement therapy to treat an AESI/imAE will be defined as time from first dose of durvalumab +/- tremelimumab to first onset of the event.

Time-to-event (TTE) is defined in months as follows:

TTE (months) = (Date of event or censoring–Date first dose of durvalumab [durvalumab + tremelimumab for the combinations modules]+1)/(365.25/12)

Time-to-resolution (TTR) of an AESI/imAE type is defined as the time from the first onset of an AESI/imAE type to the resolution of the AESI/imAE type. TTR is defined in months as follows:

TTR (months) = (Date of AESI/imAE resolution or censoring–Date of AESI/imAE onset+1)/(365.25/12)

Analysis of TTR will only include patients who have experienced an AESI/imAE.

The distribution of TTE and TTR times will be estimated using the Kaplan-Meier method (Kaplan and Meier 1958) and summarised using the median, twenty-fifth and seventy-fifth percentiles. TTE and TTR of imAE of NCI CTCAE grade >=3 will also be produced.

Deaths

A summary of deaths will present number (n) and percentage (%) of patients for the following categories:

- Total number of deaths (including deaths occurring within 90 days after last dose of study medication and deaths occurring after the 90 days post dosing window)

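### A missing day in an AE date is imputed outward, and nothing keeps these dates out of AESI duration, time to onset and time to resolution: a bias of about half a month per missing day

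*SAP*

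**What the plan says.** SAP 3.1.3 (General considerations for safety assessments) gives one set of rules for partial AE and concomitant-medication dates.

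- Onset: "If year and month are present and day is missing, impute day as first day of the month".
- End: "If year and month are present and day is missing, impute day as last day of the month".
- Death exception for end dates: "When the patient has died in the same month/year of partial stop date, use date of death".
- First-dose exception for AE onset: if the event could have begun on the first treatment date, "the AE start date will be imputed with the first study treatment date to assume a 'worst case' scenario".
- Month missing: onset becomes 1 January and end becomes 31 December. Year missing: no imputation.

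For medications the SAP names a purpose. Section 3.4.1 says: "For the purpose of inclusion in prior or concomitant mediation summaries, incomplete medication start and stop dates will be imputed". No such sentence exists for AEs.

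SAP 4.2.1 uses AE dates in three timing summaries. Under the AESI heading: "A summary of total duration (days) of AESI will be provided". Under time-to-event analyses: "Time-to-resolution (TTR) of an AESI/imAE type is defined as the time from the first onset", running to resolution. Time to onset runs from first dose to first onset. TTR and time to onset are in months, with Kaplan-Meier medians and quartiles. None of these passages excludes imputed dates or gives another date rule.

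**The concern.** Taking the earliest start and the latest end is a sensible convention when the question is whether an event could have fallen in the treatment-emergent window. It is a poor convention for measuring how long an event lasted, because both ends move outward and the two errors add. The same onset rule makes later events look as if they began sooner.

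This affects ordinary records in which month and year are known and only the day is missing. A programmer following the SAP would have one imputed date per end and would use it everywhere. With a single arm there is no comparator in which the bias could cancel, and SAP 4.1 allows that the descriptive data may support health authority considerations. Short events are distorted most in relative terms.

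**Working it through.** **Inputs.** The imputation rules and exceptions come from SAP 3.1.3, and the duration, TTR and time-to-onset definitions from SAP 4.2.1. The documents give no share of records with partial dates, so any share below is an assumption.

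**Reproducing the SAP's own example.** AE from an unknown day in June 2017 to 23 July 2017, first dose 21 June 2017. The event could have started on the first-dose date, so onset is set to 21 June 2017, as the SAP states.

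**Error per missing day, before exceptions.** If the true date is equally likely to be any calendar day, the onset error is (day of month - 1) and the end error is (days in month - day of month). Both sum to n(n-1)/2 over a month of n days. For a 365-day year:

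- seven months of 31 days: 7 x 465 = 3255
- four months of 30 days: 4 x 435 = 1740
- one month of 28 days: 378
- mean = (3255 + 1740 + 378) / 365 = 5373 / 365 = 14.7 days (range 0-30)

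In the SAP's month unit this is 14.7 / (365.25/12) = 0.48 months.

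**Both days missing.** 14.7 + 14.7 = 29.4 days. Averaging over every onset day in 2018-2019 for true durations from 3 to 180 days gives 29.4-29.5 days, or 0.97 months. The mean error hardly depends on the true duration. For example, an event from 12 to 20 March (9 days) becomes 1 to 31 March (31 days).

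**Time to onset, with the first-dose exception applied.** Averaging over all first-dose dates in the same two years:

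| True onset, study day | Mean days too early |
|---|---|
| 1 | 0 |
| 8 | 6.1 |
| 15 | 10.5 |
| 22 | 13.4 |
| 29 and later | 14.7 |

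**Effect on the reported summaries (assumed shares).**

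- Mean duration, 5% of records with one day missing: 0.05 x 14.7 = 0.7 days.
- Mean duration, 15% of records with both days missing: 0.15 x 29.5 = 4.4 days.
- Median TTR, assuming a lognormal with median 30 days and log-SD 1 and 5-20% of records affected: it moves from 30 to 31-34 days.

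**Checking the replacement rule.** Events were simulated with a true median of about 10 days and a mean of 14.9.

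- One day missing: the SAP rule gives a mean of about 29.5-29.8 days. The midpoint of the days still possible, given the other date, gives about 18. Most of the bias goes.
- Both days missing: about 60% of these events start and end in the same month. Setting both days to mid-month gives each of them a duration of 1 day, against a true mean of 7.7, and pulls the overall median down to 1 day. Midpoints must not be used for that case.

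**The case against.** The strongest reply has four parts.

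**The effect on the tables is probably small.** Protocol 6.3.3 collects start and stop dates for each AE, and Protocol 9.4 provides for queries on missing data. AEs are assessed at every four-weekly treatment visit, so partial dates should be uncommon. The documents give no frequency, and the plan is descriptive: "No hypothesis testing is planned for this single arm study". This stands, and is why the overall effect is given only as an assumed range. It does not remove the bias in whatever partial dates remain after queries.

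**The exceptions matter.** A reader might infer that the rule always yields the longest possible duration and the earliest possible onset. The SAP does not support that. In the first-dose month the onset is the first-dose date if the event could have started then, so a first-infusion reaction gets the right onset. An event that truly began before dosing in that month gets a later onset and a shorter duration. The death exception pulls in some end dates. An event with no end date is untouched by the end-date rule.

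**The primary endpoint is not at stake.** A reader might infer that timing is a named part of the primary objective. SAP 1.1.1 lists incidence, severity, nature, seriousness, intervention, outcome and causality. SAP 3.1 defines the primary outcome measure as a count and proportion of patients. Duration and timing are supporting summaries, although the duration summary sits under the AESI primary-outcome heading in 4.2.1.

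**Worst-case imputation is a declared convention.** The SAP says so for the first-dose rule. But a worst case for classification is not a justification for a duration estimate, and the SAP offers none.

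**Conclusion.** The point holds as a minor, inexpensive correction. Followed as written, the SAP biases AESI duration and AESI/imAE TTR upward and time to onset downward in records with a missing day, apart from the first-dose and death exceptions.

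The size is about half a month per missing day. It is tempting to say a month per affected event, but that is true only when both days are missing. It is also tempting to cite a median roughly doubling, but that describes only affected short events with both days missing, and no planned table shows those alone.

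The per-record figures assume that true dates are spread evenly over the calendar month. The overall figure of about 0.7-4.4 days in mean duration rests on an assumed 5-15% of AESI records being affected. AESI counts, proportions and their exact confidence intervals do not change.

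The rule for a missing month errs far more, by about 182 days on average per date before the exceptions. Such records should not enter duration or TTR on imputed dates at all.

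**What to change.** In SAP 3.1.3, state that AE dates imputed under the worst-case rules serve to classify AEs as treatment-emergent, and do not enter AESI/imAE duration, time to onset or TTR. For those three summaries, derive a second date:

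- **One day missing:** use the midpoint of the days still possible, given the other AE date, first dose (for events counted as treatment-emergent), death and DCO.
- **Both days missing, different months:** use the midpoint of each month within the same bounds.
- **Both days missing in the same month, or a month missing:** leave the record out of the duration and TTR summaries and report how many were left out.

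Footnote each table with the number of records that have an imputed day.

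The cost is a short SAP paragraph and a second derived date variable, with no new data collection. A few records drop out of duration and TTR. Those with both days in the same month tend to be short (true mean 7.7 days against 14.9 overall in the check above), so the count should be visible to the reader. The midpoint also leaves some overstatement for very short events, but much less than the present rule.

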The total number of patients to be enrolled overall and in each module will depend on the types and number of tumor modules added to the main study and country-specific ancillary studies. The number of patients and sites to be involved in individual countries will be dependent on each module or ancillary study.

It is anticipated that the total enrollment period for the overall study will be approximately 2 to 3 years, with an overall duration of 4 to 5 years.

Study design

Study Duration		Phase of Development
Estimated date of first patient enrolled (United States)	Q1 2017	Phase IIIb
Estimated date of final data cut-off (Global)	Q2 2020	
Estimated date of last patient follow up (Global) Q2		

Study Flow chart

Tumor specific modules detail which treatment regimen, combination therapy or monotherapy will be used. Patients will continue to receive study treatment as long as they are receiving clinical benefit in the opinion of the Investigator unless any of the criteria for treatment discontinuation are met first. Survival follow up will continue until the final data cut-off (DCO).

Study design

This is an open-label, multi-center, study to determine the short and long-term safety of fixed doses of durvalumab 1500 mg + tremelimumab 75 mg combination therapy or durvalumab 1500 mg monotherapy in patients with advanced solid malignancies.

This study is modular in design, each tumor specific Module allowing evaluation of the safety, tolerability, and antitumor activity of the combination of durvalumab + tremelimumab or durvalumab alone in different solid tumors.

The modules are developed as separate components appended to this protocol. Additional modules may be added as part of this protocol as decisions on additional tumor types and/or exploratory sub-studies are made.

One or more of these modules will be opened in a given country / region based on local patient population prevalence, and results of feasibility studies.

The protocol (and each tumor specific module) consists of a screening period, a treatment period, a 90–day safety follow up period, and a survival follow up period.

Patients will attend a safety follow up visit 90 days after study treatment discontinuation. Thereafter, patients will be contacted by phone or electronic communication every 3 months for survival status until the final data cut-off (DCO).

Investigational product, dosage and mode of administration

Durvalumab + tremelimumab combination therapy

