6.3.12 Safety data to be collected following the final DCO of the study

For patients continuing to receive durvalumab treatment after final DCO and database closure, it is recommended that the patients continue the scheduled site visits and Investigators monitor the patient's safety laboratory results prior to and periodically during treatment with durvalumab in order to manage AEs in accordance with the durvalumab Dose Modification and Toxicity Management Guidelines (see Section 6.9.1). All data obtained post the final DCO and database closure will be recorded in the patient notes but, with the exception of SAEs, will not otherwise be reported for the purposes of this study.

All SAEs that occur in patients still receiving durvalumab treatment (or within the 90 days following the last dose of durvalumab treatment) post the final DCO and database closure must be reported as detailed in Section 6.4.

6.4 **Reporting of serious adverse events**

All SAEs have to be reported, whether or not considered causally related to durvalumab \pm tremelimumab, or to the study procedure(s). All SAEs will be recorded in the CRF, except SAEs occurring after the DCO and database closure. After the DCO, SAEs will be reported via paper SAE forms and recorded in AstraZeneca database.

If any SAE occurs in the course of the study, then Investigators or other site personnel inform the appropriate AstraZeneca study representatives (or designees) within one day ie, immediately but **no later than 24 hours** of when he or she becomes aware of it.

The designated AstraZeneca study representative (or designee) works with the Investigator to ensure that all the necessary information is provided to the AstraZeneca Patient Safety data entry site within 1 calendar day of initial receipt for fatal and life-threatening events and within 5 calendar days of initial receipt for all other SAEs.

For fatal or life-threatening AEs where important or relevant information is missing, active follow up is undertaken immediately. Investigators or other site personnel inform AstraZeneca study representatives of any follow up information on a previously reported SAE within one calendar day ie, immediately but **no later than 24 hours** of when he or she becomes aware of it.

The reference documents for definition of expectedness are the IBs for durvalumab and tremelimumab, as applicable to the tumor specific Module.

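### Imputed end dates for adverse events and medications are not capped at the data cut-off, so a 2020 end date with no month can fall about 6 to 9 months after it

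*SAP*

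**What the plan says.** SAP 3.1.3 introduces its end-date rules with "For missing concomitant medications and AE end dates, the following will be applied". A date with no year is left alone. If the year is known but the month is not, the date becomes 31 December of that year, whether or not the day was recorded: "year and day are present and month is missing, impute as December 31st". If only the day is missing, the last day of the month is used. The single upper limit is "When the patient has died in the same month/year of partial stop date, use date of death". Nothing in the section limits an imputed end date to DCO, last contact or the end of safety follow-up.

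SAP 4.2.1 has a separate rule for the summary of AESI duration: "For ongoing AESI, the date of death or data cut-off will be imputed as end date". It also defines an analysis that runs to the end date: "Time-to-resolution (TTR) of an AESI/imAE type is defined as the time from the first onset", and ends at resolution or censoring.

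The study design table in the protocol synopsis estimates the global final DCO as Q2 2020. Protocol 6.3.12 says that data obtained after the final DCO and database closure, SAEs excepted, "will not otherwise be reported for the purposes of this study".

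**The concern.** Two rules for the same quantity, the end of an adverse event, use different limits. An event still open at DCO stops at DCO. An event known to have ended in 2020, month unknown, is carried to 31 December 2020, well beyond a Q2 2020 cut-off. The less certain record gets the longer duration, and the ordering of resolved and unresolved events can be reversed.

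Elsewhere the SAP does stop at DCO: exposure (3.1.2.1), survival censoring for patients confirmed alive or dying after DCO (3.3.1.1), and ongoing AESIs (4.2.1). The imputation rule stands out as the exception.

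The outputs exposed are those in SAP 4.2.1 that use end dates:

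- total AESI duration;
- Kaplan-Meier time to resolution for AESIs and immune-mediated events;
- AESI prevalence plots, where a patient could stay in the numerator after leaving the denominator of patients on treatment or in safety follow-up;
- length of steroid, immunosuppressant or hormone intervention, but only if imputed medication dates feed that calculation.

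Some AESI categories are rare, so a single extended record could visibly move a mean or maximum duration there.

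**Working it through.** The plan states no figure for this point, so there is none to reproduce. The check is calendar arithmetic.

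**Inputs**

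- Imputed end date for end year 2020 with no month: 31 December 2020 (SAP 3.1.3).
- Final DCO: Q2 2020, estimated (protocol synopsis). The exact day is not given, so the range 1 April to 30 June 2020 is used.
- Month length: 365.25/12 = 30.4375 days, as in the SAP 4.2.1 time-to-event formulas.
- Duration: end date − onset date + 1, as in the SAP formula for time to resolution. Using it for the duration summary too is an assumption, because the SAP gives no separate formula there.

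**Step 1. Overshoot past DCO** = 31 December 2020 − DCO

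| DCO | Days past DCO | Months |
|---|---|---|
| 1 April 2020 | 274 | 274/30.4375 = 9.00 |
| 15 May 2020 | 230 | 230/30.4375 = 7.56 |
| 30 June 2020 | 184 | 184/30.4375 = 6.05 |

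**Step 2. Resolved against ongoing, same onset**

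| Onset | DCO | Resolved in 2020, month unknown (days) | Ongoing, closed at DCO (days) | Ratio |
|---|---|---|---|---|
| 1 March 2020 | 1 April 2020 | 305 + 1 = 306 | 31 + 1 = 32 | 9.56 |
| 1 March 2020 | 30 June 2020 | 306 | 121 + 1 = 122 | 2.51 |
| 1 October 2019 | 1 April 2020 | 457 + 1 = 458 | 183 + 1 = 184 | 2.49 |
| 1 October 2019 | 30 June 2020 | 458 | 273 + 1 = 274 | 1.67 |

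Whatever the onset, the resolved record exceeds the ongoing one by the Step 1 overshoot, 184 to 274 days.

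**Step 3. Day missing, month known.** The last day of the month can pass DCO only if the event ended in the DCO month. The largest gap in Q2 is 31 May − 1 May = 30 days.

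**Step 4. With a cap at DCO.** The overshoot is 0 days. The event with onset 1 March 2020 gets at most 32 to 122 days instead of 306, the same as an ongoing event.

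**Which records are reached.** The large overshoot needs all of the following: end year 2020; no month; and a patient not covered by the death rule. A 31 December imputation in any earlier year cannot pass a Q2 2020 DCO. The death rule may help some patients who died in 2020, but its condition of the same month/year is ambiguous when the month is the missing part.

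**The case against.** The case for leaving the rule alone has several parts.

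*Primary outcome.* Because SAP 4.2.1 places AESI duration under its primary-outcome heading, a reader might infer that the primary result is biased. The documents do not support that. SAP 3.1 defines the primary outcome measure as the number and proportion of patients with an AESI, and neither that proportion nor its exact interval uses an end date. This part of the objection stands in full.

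*Frequency.* Start and stop dates are collected for every event (Protocol 6.3.3), events are assessed at each treatment visit (4.2.2), and missing data are to be queried (9.4). Few month-less 2020 records should survive. That lowers the count but leaves the rule as it is.

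*Effect on results.* Time to resolution is summarised by the median and quartiles, which a few late dates may not move. No effect on a reported statistic can be shown from the documents, so the summaries could be inflated; it does not follow that they would be.

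*Medication dates.* SAP 3.4.1 gives the purpose of imputing them as classification into prior or concomitant summaries, where a late end date does no harm. SAP 4.2.1 bases length of intervention on start and stop dates without mentioning imputation. SAP 3.1.3 is worded generally, so the extension to steroid duration is possible but remains an inference.

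*Whether the dates are impossible.* A reader might say that the data cannot contain a date after DCO. The DCO is an estimate, its definition is left to the modules (Protocol 9.3), and Protocol 6.3.12 excludes data after DCO and database closure jointly. The documents do not expressly bar an end date between the two. What can be said is that the imputed date lies 6 to 9 months past the estimated cut-off.

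*Convention.* Late imputation of partial end dates is a deliberate worst-case choice, and "No hypothesis testing is planned for this single arm study". That explains the use of 31 December. It does not explain giving a resolved event more time than one that never resolved.

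**Conclusion.** The rule is wrong as written, and the consequence is minor. SAP 3.1.3 can date the end of an event or medication 184 to 274 days (about 6 to 9 months) past DCO, and by at most 30 days when only the day is missing. It can also reverse the order of resolved and unresolved AESIs in the duration summary.

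This rests on a final DCO in Q2 2020, as estimated, and on the 31 December rule being programmed literally. It is not a finding about every event that ended in 2020: only those with no recorded month get the large overshoot. Their number is not given, so the effect on any median or mean cannot be sized. The exposed results are descriptive: AESI duration, time to resolution, prevalence plots and, conditionally, length of intervention. AESI incidence is not materially affected.

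**What to change.** Add one sentence to SAP 3.1.3, applying to both adverse events and concomitant medications: *Imputed end dates are the earliest of the imputed date, date of death, and DCO.*

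This covers the month-missing and day-missing rules together, removes the ambiguity in the death condition, and brings the section into line with the treatment of ongoing AESIs in SAP 4.2.1. It needs no new data and leaves the definition of every endpoint unchanged. The cost is one sentence and the matching line of programming; if no such record exists, no result changes.
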